7.4 Subgroup Analyses

The analysis for the primary efficacy parameter will be performed within each category of the following:

- Age group (< 55 years, \geq 55 years)
- Sex (male, female)
- Race (white, all other races)
- Region (US, Non-US)

7.5 Sample Size Calculation

The sample size and power calculations are based on the analysis of time to relapse in the DB treatment period to compare each cariprazine dose group versus placebo based on a log-rank test. The trial will be a fixed follow-up design. Patients are followed from randomization until dropout, relapse or a fixed duration of 26 weeks.

Based on the first 26 weeks' data from RGH-MD-06, the relapse hazard ratio is assumed to be 0.50, and cumulative relapse rate at Week 26 for the placebo group is 46% (Study RGH-MD-06, 2015). In addition, the cumulative dropout rate due to reasons other than relapse at 26 weeks is assumed to be 20.0%.

Using these assumptions, a total of approximately 103 in the DB phase need to be observed in order to have 85% power to detect a statistically significant difference between each cariprazine and placebo group, using 2-tailed, log-rank tests at an overall 5% level of significance. The trial should randomize approximately 345 patients, 115 patients each arm, to provide the required number of relapse events. EAST 6.0 was used to for sample size and power calculation.

A fixed-sequence procedure will be used for multiple comparisons to control the family-wise Type I error rate at a 0.05 level. First, the cariprazine 4.5 mg/d group will be compared with

the placebo group in the primary endpoint; if the testing is significant at the 0.05 level, then cariprazine 3.0 mg/d arm will be compared with the placebo group.

Assume the screening failure rate is 34%, and approximately 33.3% of patients enrolled into the OL treatment period will be randomized into the DB treatment period. Then, approximately 1035 patients will be expected to be enrolled into the OL treatment period, and approximately 1569 patients are expected to be screened.

7.6 Interim Analyses

No formal interim analysis is planned.

8 Study Visit Schedule and Procedures

[Table 1](#) and [Table 2](#) present the study visits and procedures for OL and DB periods in the study.

8.1 Patient Entry Procedures

8.1.1 Overview of Entry Procedures

Prospective patients as defined by the criteria in [Sections 4.3](#) and [4.4](#) (inclusion/exclusion criteria) will be considered for entry into this study.

8.1.2 Informed Consent and Subject Privacy

The study will be discussed with the patient and/or the patient's legally authorized representative, and a patient wishing to participate must give informed consent prior to any study-related procedures or change in treatment. The patient must also give authorization (United States only), data protection consent (Europe only), and other written documentation in accordance with the relevant country and local privacy requirements (where applicable) prior to any study-related procedures or change in treatment.

Each patient that provides informed consent will be assigned a patient number that will be used on patient documentation throughout the study.

Where applicable, a central vendor will be used to verify patients' current and past research study status in order to mitigate safety concerns associated with duplicate enrollment and protocol deviations associated with multiple trial enrollment. Following proper informed consent and after issuing a patient number, each patient will be checked in the Verified

Clinical Trials database, indicated in the Schedule of Visits and Procedures ([Table 1](#)). Partial patient identifiers will be utilized but will not be accessible to the sponsor. Patients who are identified as verification failures by VCT should not continue in trial without documented approval from the sponsor.

8.2 Washout Intervals/Run-in

Patients will undergo a Screening/washout period of up to 7 days. The length and timing of the washout of prior psychiatric medications during the 7 days allotted for the Screening period is at the discretion of the investigator. Prior medications should be gradually withdrawn such that the washout is completed by Visit 2/Baseline. Please note that during the screening/washout period, psychotropic medications, other than those listed as rescue ([Section 4.8.3](#)), may not be newly initiated or reinstated. In order to ensure the safe transition of patients into the study, based upon the clinical judgment of the investigator, patients may be hospitalized during initiation of the study. This hospitalization can be for up to 14 days during the screening and OL periods (with the end of hospitalization no later than Visit 3 [Day 8] of the OL treatment period). This 14-day allowance for hospitalization may include all or part of the Screening period. Hospitalization beyond the initial 14 days allowed will require consultation with the medical monitor. Following the protocol-allowed 14 days of hospitalization (and any sponsor-allowed extension), patients should be treated as outpatients.

No run-in period will be used in this study.

8.3 Procedures for Final Study Entry

Patients meeting all eligibility criteria to continue into the OL treatment period at Visit 2 (Baseline) must meet the stability criteria specified in [Section 4.5](#) and randomization criteria specified in [Section 4.6](#) to be eligible for randomization (Visit 13). Rescreening of screen failures is permitted in certain situations after consultation with the Allergan medical monitor.

Also, all females of childbearing potential must have negative qualitative results on the serum pregnancy test at the Screening Visit (Visit 1).

See [Section 5.4](#) for the method for assignment to treatment groups/randomization.

8.4 Visits and Associated Procedures

All assessments will be conducted at the appropriate visits as outlined in [Table 1](#) and [Table 2](#) and the timing of the visits should occur as close as possible to the specified day.

Visit 2/Baseline is expected to occur within 7 days of Visit 1; however, if required it may be conducted up to 3 days after the scheduled visit.

If necessary, Visits 3 to 28 may be conducted up to 3 days before or after the scheduled visits. The visit windows for each scheduled visit are relative to Visit 2 for Visits 3 through 13, relative to Visit 13 for Visits 14 through 26/ET, and relative to Visit 26/ET for Visits 27 and 28.

The schedule of study procedures and assessments is displayed by visit in [Table 1](#) and [Table 2](#). The descriptions of the procedures to be performed at each visit are provided below.

8.4.1 Screening/Visit 1 (Days -7 to -1)

The following procedures will be performed at Screening (Visit 1):

- Obtain informed consent and patient privacy; consent for pharmacogenetic sampling may also be obtained
- Verified Clinical Trials database check to be performed where applicable
- Access IWRS to register the patient and assign a PID number
- Assess inclusion/exclusion criteria
- Collect and assess medical and psychiatric history
- Administer and assess SCID-5
- Collect blood sample for hepatitis screening
- Collect samples for UDS; assess blood alcohol concentration via breathalyzer
- Collect blood samples for clinical laboratory determinations
- Collect blood samples for serum pregnancy test (women of childbearing potential only)
- Collect blood sample for hemoglobin A1c
- Review prior and concomitant medications

- Administer SCI-PANSS, CGI-S, and C-SSRS
- Collect vital signs measurements, including weight, waist circumference, and height
- Perform physical examination
- Perform ECG
- Review and assess AEs and SAEs
- Perform ophthalmological examination (Note: The screening ophthalmological examination must be completed prior to Visit 2/Baseline and the start of OL IP.)

8.4.2 Baseline/Visit 2

The following procedures will be performed at Baseline /Visit 2:

- Review and assess AEs and SAEs
- Review concomitant medications
- Assess inclusion/exclusion criteria
- Administer SCI-PANSS, BACS, CGI-S, PSP, and C-SSRS
- Evaluate EPS symptoms (AIMS/BARS/SAS)
- Collect vital signs measurements (including weight)
- Obtain consent for and/or collect blood for pharmacogenetic sampling (consent for pharmacogenetic sampling may be obtained any time between Visit 1 and Visit 8, inclusive. For patients providing consent, the sample for pharmacogenetic testing must be obtained between Visit 2 and Visit 8, inclusive)
- Access IWRS to dispense IP

8.4.3 Open-label Treatment Period (Visits 3 to 12)

The following procedures will be performed during the OL treatment period at every visit except where noted:

- Review concomitant medications

- Collect vital signs measurements (including weight)
- Collect waist circumference measurement (only Visit 9)
- Administer SCI-PANSS, CGI-S, CGI-I, and C-SSRS
- Assess PSP (only Visit 8)
- Evaluate patients for attainment of response threshold criteria (Section 4.5). Continue to assess between Visits 6 to 8 until criteria have been met. Patients not meeting response threshold criteria by Visit 8 should be discontinued and undergo procedures as for Visit 26/ET and subsequently complete the SFU period
- At Visits 7 through 9, evaluate patients for attainment of response threshold criteria (Section 4.5) if response threshold criteria were met at the preceding visit.
 - Patients who have not met stability of response threshold criteria by Week 10 (Visit 9) should be discontinued and undergo procedures as for Visit 26/ET and subsequently complete the SFU period
 - Patients who have met stability of response threshold criteria (Section 4.5) must maintain stability threshold for 8 consecutive weeks in order to be randomized, with allowance for 1 excursion
 - For patients who have met stability of response threshold criteria, evaluate randomization criteria (Section 4.6) 8 weeks after stability of response threshold criteria are met (may be as early as Visit 11). Patients who meet randomization criteria (Section 4.6) prior to Visit 13 are to undergo procedures specified for Visit 13/End of OL treatment period (Section 8.4.4; any remaining visits in the OL treatment period will be skipped).
 - Patients who have attained stability of response threshold criteria and who meet any of the following criteria will be discontinued and should undergo Visit 26/ET procedures and subsequently complete the SFU period:
 - PANSS total score increases by $\geq 30\%$ relative to Visit 2/Baseline, or
 - Score > 4 on 1 or more of 7 PANSS items P1: delusions; P2: conceptual disorganization; P3: hallucinatory behavior; P6: suspiciousness/persecution; P7: hostility; G8: uncooperativeness; or G14: poor impulse control, or

- Patients who have an increase in CGI-S score by 2 or more points relative to Visit 2/Baseline
- Evaluate EPS symptoms (AIMS/BARS/SAS) (Visits 3, 7, 9, and 11)
- Collect blood samples for serum pregnancy test (women of childbearing potential only) (Visit 8)
- Collect blood samples for clinical laboratory determinations and for hemoglobin A1c (Visit 8)
- Collect IP blister card(s) and perform IP compliance and accountability
- Obtain consent for and collect blood for pharmacogenetic sampling (consent for pharmacogenetic sampling may be obtained any time between Visit 1 and Visit 8, inclusive. For patients providing consent, the sample for pharmacogenetic testing must be obtained between Visit 2 and Visit 8, inclusive)
- Review and assess AEs and SAEs
- Access IWRS to dispense IP

8.4.4 End of Open-label Period/Randomization Visit (Visit 13)

The following procedures will be performed at Visit 13:

- Review concomitant medications
- Collect vital signs measurements, including weight
- Measure waist circumference
- Administer SCI-PANSS and CGI-S to determine whether randomization criteria (Section 4.6) have been met
 - Eligible patients: Access IWRS to randomize patient and dispense DB IP
 - Patients who do not meet randomization criteria are to undergo procedures as for Visit 26/ET and scheduled to return for the SFU Visits (Visit 27 and Visit 28)
- Assess C-SSRS, BACS, CGI-I, and PSP

- Evaluate EPS symptoms (AIMS/BARS/SAS)
- Perform ECG
- Perform ophthalmological examination. NOTE: For patients eligible for randomization, every attempt should be made to complete the Visit 13 ophthalmological examination on the same day as all other Visit 13 procedures. If the examination cannot be accommodated, it must occur within 7 days after randomization.
- Collect samples for UDS; assess blood alcohol concentration via breathalyzer
- Collect blood samples for clinical laboratory determinations
- Collect blood samples for serum pregnancy test (women of childbearing potential only)
- Collect blood sample for hemoglobin A1c
- Review and assess AEs and SAEs
- Collect IP blister cards and perform IP compliance and accountability
- Access IWRS to dispense IP

8.4.5 Double-blind Treatment Period (Visits 14 to 25)

The following procedures will be performed during the DB treatment period at every visit except as noted:

- Review concomitant medications
- Collect vital signs measurements (including weight)
- Collect waist circumference measurement (Visit 19)
- Administer SCI-PANSS and CGI-S and assess patient for relapse (per [Section 4.7](#))
- Assess CGI-I and C-SSRS
- Assess PSP (Visits 16 and 20)

- Assess BACS (Visit 16)
- Evaluate EPS symptoms (AIMS/BARS/SAS) (Visits 15, 17, 19, 21, and 23)
- Assess patient for relapse (Section 4.7)
- Collect blood samples for clinical laboratory determinations (Visits 18 and 22)
- Collect samples for serum pregnancy test (women of childbearing potential only) (Visits 18 and 22)
- Review and assess AEs and SAEs
- Collect IP blister cards and perform IP compliance and accountability
- Access IWRS to dispense IP

8.4.6 Final or Early Termination Visit (Visit 26)

The following procedures will be performed at the final visit at the end of the DB treatment period (Visit 26) or at ET:

- Review concomitant medications
- Collect vital signs measurements, including weight and waist circumference
- Administer SCI-PANSS, BACS, CGI-S, CGI-I, PSP, and C-SSRS
- Evaluate EPS (AIMS/BARS/SAS)
- Assess patient for relapse (Section 4.7)
- Perform physical examination
- Perform ECG
- Perform ophthalmological examination.
NOTE: every attempt should be made to complete the Visit 26/ET ophthalmological examination on the same day as all other Visit 26/ET procedures.
- Collect blood samples for clinical laboratory determinations

- Collect sample for hemoglobin A1c
- Collect sample for serum pregnancy test (women of childbearing potential only)
- Review and assess AEs and SAEs
- Collect IP blister card(s) and perform IP compliance and accountability

8.4.7 Safety Follow-up Visits (Visits 27 and 28)

Patients who complete the study, and those who prematurely discontinue from either the OL or DB treatment periods, will complete a 4-week SFU period (2 visits: one at the end of every 2 weeks). During the SFU period, patients will be stabilized on appropriate medications, and additional evaluations (laboratory studies, ECG, UDS, etc) may be performed as deemed necessary by the investigator. This period may also be used for follow-up and management of all abnormal findings and AEs observed during OL or DB treatment periods. No IP will be administered during the SFU period.

The following procedures will be carried out at the SFU Weeks 46 and 48 (Visits 27 and 28):

- Collect blood sample for serum pregnancy test (women of child-bearing potential only [Visit 28 only])
- Review concomitant medications
- Collect vital signs measurements (including weight)
- Perform a follow-up ophthalmological examination only for patients with a postbaseline finding of cataracts (Visit 28 only)
Note: Every attempt should be made to complete the Visit 28 ophthalmological examination on the same day as all other Visit 28 procedures. If the examination cannot be accommodated, it must occur within 7 days of Visit 28.
- Review and assess AEs and SAEs

8.5 Instructions for Patients

Patients are to be instructed to take their study medication daily around the same clock time; study medication should not be taken with grapefruit juice. Patients are to be reminded to return used/partially used blister cards at every study visit. The investigator (or designee) is to ensure that concomitant medications are reviewed against the prohibited and allowed

rescue medications detailed in [Section 4.8](#); patients are to be advised accordingly. If the permissibility of a specific medication/treatment is in question, the investigator should consult the medical monitor.

Patients are to be asked to abstain from drinking alcohol during the study.

Patients are to be asked to fast for at least 10 hours before blood and urine samples are collected at Screening (Visit 1), Visits 8, 13 (End of OL/Randomization), 18, 22, and 26/ET.

8.6 Unscheduled Visits

Additional examinations and laboratory assessments may be performed as necessary to ensure the safety and well-being of the patients during the study period. Unscheduled visit eCRF pages will be completed for each unscheduled visit. For all parameters not measured, indicate “not done.”

8.7 Compliance with Protocol

All assessments will be conducted at the appropriate visits as outlined in [Table 1](#) and [Table 2](#) and the timing of the visits should occur as close as possible to the specified day.

Visit 2/Baseline is expected to occur within 7 days of Visit 1. If required, Visit 2/Baseline assessments may be conducted up to 3 days after the scheduled visit. If necessary, Visits 3 to 28 may be conducted up to 3 days before or after the scheduled visits. The visit windows for each scheduled visit are relative to Visit 2 for Visits 3 through 13, relative to Visit 13 for Visits 14 through 26/ET, and relative to 26/ET for Visits 27 and 28. Every attempt should be made to complete the postbaseline ophthalmological examinations (Visits 13 and Visits 26/ET, and Visit 28 if required) on the same date as all other study procedures for that visit. At each visit, the patient will be asked if the patient changed the dose/regimen of any existing concomitant medications or initiated the use of any new concomitant medications since the last visit to ensure compliance with the protocol.

8.8 Early Discontinuation of Subjects

Patients may discontinue from the study at any time for any reason. Discontinuation is permanent; once a patient is discontinued, he/she shall not be allowed to enroll again.

Patients can be prematurely discontinued for one of the following reasons:

- AE

- Noncompliance with protocol
- Noncompliance with IP dosing regimen
- Withdrawal of consent (a clear reason must be documented when possible)
- Lost to follow-up (every effort must be made to contact the patient; a certified/traceable letter must be sent)
- Study terminated by sponsor
- Site terminated by sponsor
- Pregnancy
- Other reasons

Notification of early patient discontinuation from the study and the reason for discontinuation will be clearly documented on the appropriate eCRF page. Patients who take IP during the study (OL treatment period or the DB treatment period) and who prematurely discontinue from the study, regardless of cause, should be seen for a final assessment. A final assessment will be defined as completion of the evaluations scheduled for Visit 26/ET. If the patient discontinues after IP is taken, the patient is also expected to return for the SFU Visits (Visit 27 and Visit 28) 2 weeks and 4 weeks after completion of the ET visit.

At a minimum, collect the following information when a patient discontinues:

1. The reason the patient discontinued;
2. The date of the last dose of IP from the trial;
3. The date of the last assessment and/or contact. A follow-up contact (telephone or visit) will be arranged as appropriate;
4. (S)AEs;
5. Compliance with the IP administration as specified in this protocol;
6. Final Assessments: Unless there is withdrawal of consent, every effort should be made to ensure that all procedures and evaluations scheduled for Visit 26/ET and subsequently Visit 27 and Visit 28 (SFU Visits) are performed ([Table 2](#), Schedule of Visits and Procedures).

7. Retrieve IP from the patient.

For all patients who discontinue as a result of being lost to follow-up, a determination must be noted in the eCRF as to whether the loss is related to an acute exacerbation of schizophrenia.

8.9 Withdrawal Criteria

It is the right and the duty of the investigator or subinvestigator to stop treatment in any case in which emerging effects are of unacceptable risk to the individual patient. In addition, the investigator or subinvestigator is to stop treatment of any patient with unmanageable factors that may interfere significantly with the trial procedures and/or the interpretation of results.

A patient must be discontinued for any of the following reasons:

1. The patient is unable to tolerate the 4.5 mg/d dose.
2. The patient fails to attain *response threshold* by Week 8 (Visit 8) or stability of response threshold criteria by Week 10 (Visit 9) (see [Section 4.5](#));
3. After stability has been attained, except for the single allowed excursion above the response threshold prior to Visit 13/End of OL, there is a lack of ongoing stability as evidenced by PANSS total score increases by $\geq 30\%$ relative to Visit 2/Baseline; or PANSS item score is > 4 on one or more of PANSS items P1: delusions; P2: conceptual disorganization; P3: hallucinatory behavior; P6: suspiciousness/persecution; P7: hostility; G8: uncooperativeness; G14: poor impulse control; or CGI-S score increases by 2 or more points relative to Baseline/Visit 2;
4. The patient required or initiated hospitalization for his/her psychiatric symptoms (excluding the discretionary hospitalization stay, which is to end no later than Visit 3 [Day 8] of the OL treatment period, or extension of the initial hospitalization described in this protocol);
5. The patient took or required prohibited medication, including initiation of treatment with a mood stabilizer, antidepressant, antipsychotic agent, or with a benzodiazepine that exceeds the protocol-specified allowance or duration (ie, more than 2 mg/d of lorazepam or equivalent or for more than 3 consecutive days) to treat worsening symptoms of schizophrenia or any other psychiatric disorder as judged by the clinical impression of the investigator;

6. At the end of the OL treatment period, the patient does not meet all criteria to enter the DB treatment period ([Section 4.6](#));
7. Positive UDS after enrollment, confirmed by retest at next scheduled visit; for exceptions see [Exclusion Criterion 3](#) and [Section 4.8.3](#);
8. The patient meets the criteria for relapse during the DB treatment period;
9. The patient experiences 1 of the following elevated liver enzyme conditions, which is confirmed by repeat testing within 48 to 72 hours of awareness:
 - ALT or AST $> 3 \times$ ULN and total bilirubin $> 2 \times$ ULN,
 - ALT or AST $> 8 \times$ ULN,
 - ALT or AST $> 5 \times$ ULN for more than 2 weeks,
 - ALT or AST $> 3 \times$ ULN with the appearance of jaundice, worsening of fatigue, nausea, vomiting, right upper quadrant pain or tenderness, fever, rash, or eosinophilia.
10. The patient has an absolute neutrophil count of < 1000 per mm^3 and, after repeat testing within 24 hours of awareness, the values are not normalized or are not increasing;
11. A female patient becomes pregnant during treatment.

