Once stability has been achieved, patients must continue to meet the response threshold criteria for an additional 8 weeks (ie, maintenance of stability) to qualify for randomization. During the maintenance of stability period, one excursion outside the response threshold criteria will be allowed. The excursion may occur at any time during the 8-week period with the exception of Visit 13/End of OL, but must be followed by a return to response threshold at the next visit. In the event the excursion occurs in a patient's 8th week of stability, but prior to Visit 13/End of OL, the patient should be assessed at the following scheduled visit to confirm whether randomization criteria have been met.

Patients who do not meet the response threshold criteria by Week 8 (Visit 8) or stability criteria by Week 10 (Visit 9) will be discontinued. Additionally, patients who at any time require either hospitalization (excluding protocol-allowed hospitalization during

Screening/OL periods for the purpose of washout of prior psychiatric medications) or initiation of treatment with a mood stabilizer, antidepressant, antipsychotic agent, or with a benzodiazepine that exceeds the protocol-specified allowance or duration (ie, more than 2 mg/d of lorazepam or equivalent or for more than 3 consecutive days) to treat worsening symptoms of schizophrenia or any other psychiatric disorder as judged by the clinical impression of the investigator will be discontinued.

During the 8-week maintenance of stability period, patients who meet any of the following will be discontinued and will subsequently enter the SFU period:

- PANSS total score increases by $\geq 30\%$ relative to Visit 2/Baseline, or
- Score > 4 on 1 or more of the following 7 PANSS items: P1: delusions; P2: conceptual disorganization; P3: hallucinatory behavior; P6: suspiciousness/persecution; P7: hostility; G8: uncooperativeness; G14: poor impulse control, or
- Have an increase in CGI-S score by 2 or more points relative to Visit 2/Baseline

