 - d. History of amiodarone or systemic corticosteroid use for \geq 3 consecutive months in the past year

- e. Intraocular pressure of > 21 mm Hg in either eye
- f. Unable to dilate pupil to at least 5 mm in either eye

19. Allergies to dilating drops, optic medications, or topical ocular anesthetics that are to be used in the ophthalmological examination.

20. Known human immunodeficiency virus infection.

21. Positive hepatitis C antibody on screening.

22. Positive test for hepatitis B surface antigen and/or hepatitis B core antibody immunoglobulin M on screening.

23. Screening liver enzyme test (aspartate aminotransferase [AST] and/or alanine aminotransferase [ALT]) results $> 2 \times$ the upper limit of normal (ULN) or total bilirubin $> 1 \times$ ULN.

24. Absolute neutrophil count < 1000 per mm³ at screening.

25. Hemoglobin A1c (HbA1c) $> 7\%$ at screening.

26. Blood alcohol concentration ≥ 0.02 g/dL at Visit 1 as measured by breathalyzer.

27. History of tardive dyskinesia (except for mild cases attributed to use of conventional agents), serotonin syndrome, or neuroleptic malignant syndrome.

Other Criteria:

28. Employee, or immediate relative of an employee, of the sponsor, any of its affiliates or partners, or the study center.

29. Inability to speak, read, or understand the local language sufficiently to understand the nature of the study, to provide signed written informed consent, or to allow the completion of all study assessments.

30. Unable or unlikely to comply with the study protocol or unsuitable for any other reason, as judged by the investigator.

4.5 Response Threshold, Stability, and Maintenance of Stability Criteria During the OL Treatment Period

Response threshold is defined as meeting all of the following criteria on or after Week 4 (Visit 6):

- PANSS total score ≤ 60 , and
- $\geq 20\%$ decrease in PANSS total score from Visit 2/Baseline, and
- Score of ≤ 4 on each of the following 7 PANSS items:
 - P1: delusions
 - P2: conceptual disorganization
 - P3: hallucinatory behavior
 - P6: suspiciousness/persecution
 - P7: hostility
 - G8: uncooperativeness
 - G14: poor impulse control; and
- CGI-S ≤ 4
- No significant tolerability issues as judged by the investigator

Note: Patients who do not meet the response threshold criteria by Week 8 (Visit 8) will be discontinued and undergo early termination (ET) procedures and subsequently complete the SFU period.

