Stability is the reconfirmation of response threshold criteria at either the visit following first attainment of response threshold or, in the event of an excursion, at the second visit following first attainment. One clinical excursion outside of the response threshold range is allowed between the first attainment of response threshold criteria and the subsequent confirmation of it (ie, stability). Following the excursion, patients not meeting response threshold criteria must be discontinued and undergo ET procedures and subsequently complete the SFU period.

Note: Patients who do not meet stability criteria by Week 10 (Visit 9) will be discontinued and undergo ET procedures and subsequently complete the SFU period.

Maintenance of stability criteria: Once stability has been attained, patients must continue to meet response threshold criteria for 8 additional weeks. One excursion of response threshold is allowed during the 8-week period, provided that it does not occur at Visit 13/End of OL. If an excursion occurs, the response threshold criteria must be met at the subsequent visit. Patients not meeting response threshold criteria at the visit following an excursion must be discontinued and undergo ET procedures and subsequently complete the SFU period.

Note: If any of the following occurs after stability has been established (ie, during the 8-week maintenance of stability period), the patient is to be discontinued:

- PANSS total score increases by $\geq 30\%$ relative to Visit 2/Baseline; or
- Score is > 4 on 1 or more of the following 7 PANSS items: P1: delusions; P2: conceptual disorganization; P3: hallucinatory behavior; P6: suspiciousness/persecution; P7: hostility; G8: uncooperativeness; G14: poor impulse control; or
- CGI-S score increases by 2 or more points relative to Baseline/Visit 2; or
- Hospitalization is required (excluding protocol-allowed hospitalization during Screening/OL periods for the purpose of washout of prior psychiatric medications); or
- Initiation of treatment with a mood stabilizer, antidepressant, antipsychotic agent, or with a benzodiazepine that exceeds the protocol-specified allowance or duration (ie, more than 2 mg/d of lorazepam or equivalent or for more than 3 consecutive days) to treat worsening symptoms of schizophrenia or any other psychiatric disorder as judged by the clinical impression of the investigator

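### Sections 3.2, 4.5 and 8.4.3 and the Protocol Summary discontinue a patient for a PANSS item score above 4 during maintenance of stability; Section 8.9 exempts the one allowed excursion from that same trigger

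*Protocol*

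**What the plan says.** Section 4.5 defines the response threshold by several conditions that must all hold. One of them is "Score of ≤ 4 on each of the following 7 PANSS items". The others are a PANSS total of at most 60, a fall of at least 20% from Visit 2, CGI-S of at most 4, and no significant tolerability problem.

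For the 8 weeks after stability, Section 3.2 states "During the maintenance of stability period, one excursion outside the response threshold criteria will be allowed", and Section 4.5 states "One excursion of response threshold is allowed during the 8-week period, provided that it does not occur at Visit 13/End of OL". Both require the threshold to be met again at the following visit.

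The same sections then set discontinuation triggers. Section 3.2 has "During the 8-week maintenance of stability period, patients who meet any of the following will be discontinued", and its list includes "Score > 4 on 1 or more of the following 7 PANSS items" together with the PANSS total and CGI-S triggers. Section 4.5 has "If any of the following occurs after stability has been established (ie, during the 8-week maintenance of stability period), the patient is to be discontinued", followed by the same three triggers and two others. The Protocol Summary and Section 8.4.3 repeat the pattern.

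Section 8.9 item 3 gives the same three triggers as a reason for mandatory discontinuation, but begins "After stability has been attained, except for the single allowed excursion above the response threshold prior to Visit 13/End of OL".

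**The concern.** An item score above 4 breaches one component of the threshold, so by the protocol's own definition it is an excursion. Four texts say that such a patient leaves the study. The fifth says that the first such event before Visit 13 is not a reason to leave. A site could follow either and be able to cite the protocol.

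The decision cannot be undone, because Section 8.8 makes discontinuation permanent. At stake are three things: which patients reach randomisation, how many open-label patients are needed to supply them, and whether a given patient is recorded as a withdrawal-criteria deviation, a category that SAP Section 7.2 requires to be summarised.

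**Working it through.** The main check is a comparison of texts.

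| Text | One excursion allowed in the 8 weeks? | Item > 4, PANSS total up ≥ 30% or CGI-S up ≥ 2 | Exemption for the allowed excursion? |
|---|---|---|---|
| Protocol Summary | Yes | Discontinue | None |
| Protocol 3.2 | Yes | Discontinue | None |
| Protocol 4.5 | Yes, not at Visit 13 | Discontinue | None |
| Protocol 8.4.3 | Yes | Discontinue | None |
| Protocol 8.9 item 3 | Yes, before Visit 13 | Discontinue | Yes |
| Protocol 4.6 | Not mentioned | Not listed as triggers | Not addressed |
| SAP 4.0 and Table 4-1 | Yes | Not mentioned | Not addressed |

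No text gives one section precedence over another.

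**Worked case.** A patient first meets the threshold at Visit 6 (Week 4) and confirms it at Visit 7 (Week 6), so the 8 weeks run to Visit 11 (Week 14). At Visit 9 (Week 10), P1 is 5 and every other component is met. At Visit 10 and Visit 11 the full threshold is met.
- Under the Protocol Summary, 3.2, 4.5 and 8.4.3, the patient is discontinued at Visit 9.
- Under 8.9 item 3, Visit 9 is the single allowed excursion. The patient stays and can be randomised at Week 14.

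**Which trigger is likely to matter.** Inclusion criterion 6 requires a PANSS total of at least 70 at Visit 2. A 30% rise therefore means at least 70 × 1.30 = 91. With a baseline of 70, the threshold total is at most 70 × 0.80 = 56, so this trigger needs a jump of at least 91 − 56 = 35 points; higher baselines need more. The item trigger needs one item to move from 4 to 5. In practice the conflict is mainly about the item score, although the 8.9 exemption covers all three triggers.

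**The plan's own figures.** Section 7.5 assumes that 33.3% of open-label patients are randomised and 34% fail screening: 345 × 3 = 1035, and 1035 / 0.66 = 1568 (stated as 1569). These reproduce. The plan does not say which discontinuation rule the 33.3% presumes. Section 4.1 continues enrolment until about 115 per arm are randomised, so a lower yield would raise the number entering open-label treatment, not lower the planned number randomised.

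**A related wording point.** Section 8.4.3 directs the stability check at Visits 7 to 9 to patients "if response threshold criteria were met at the preceding visit". A patient who first meets the threshold at Visit 7 and has an excursion at Visit 8 did not meet it at the visit before Visit 9. Section 4.5 and Table 1 footnote g nevertheless provide for reassessment at Visit 9. The footnote largely settles the intent; the 8.4.3 wording is simply out of line with it.

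**The case against.** The best counter-reading is that the allowed excursion covers only components that are not triggers, such as a PANSS total above 60 or a fall of less than 20%. That makes the Protocol Summary, 3.2, 4.5 and 8.4.3 coherent, and it is four texts against one clause. It does not rescue 8.9: the exemption there is attached to the triggers themselves, and on this reading it would have almost nothing to exempt. The conflict is narrowed, not removed.

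Other limits on the point stand in full.
- A reader might infer that the treatment comparison is compromised. It is not. The decision comes before randomisation, which SAP Section 4.0 stratifies by site in blocks of 3.
- A reader might infer that sites randomise materially different populations, with a different relapse risk, because an item score above 4 is also a relapse event under Section 4.7. The documents give no data on that. Every eligible patient must meet the full threshold at Visit 13, so the difference is one earlier transient score.
- A reader might want a count of affected patients. Any count would come from multiplying 345 by an assumed share that no document supports.
- A reader might infer that deviations cannot be classified consistently. SAP Section 7.2 has important deviations reviewed and documented before database lock and unblinding, so one review can apply one rule. It does need to be told which.

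Early termination (SAP Section 4.0) also means that new protocol wording can do little for conduct in this trial. The abbreviated report in SAP Appendix IV still contains the primary efficacy analysis and a listing of protocol deviations, so the SAP side remains live.

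**Conclusion.** The contradiction is real and follows from the text alone: the same patient gets opposite outcomes on an irreversible decision, and nothing in either document resolves it. The consequence is limited to the composition of the randomised population, the randomisation yield and the classification of withdrawal-criteria deviations. The validity of the between-arm comparison is not in question. How many patients are affected is unknown, because the documents give no frequency of single item scores above 4 after stability. The conclusion rests on reading an excursion as failure of any component of the threshold, which is how Section 4.5 is worded.

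**What to change.** **Protocol.** Reconcile the Protocol Summary and Sections 3.2, 4.5, 8.4.3 and 8.9 so that all five state the same rule for the item-score, PANSS total and CGI-S triggers during the one allowed excursion. The clinical team must decide which rule governs. Bring the 8.4.3 condition about the preceding visit into line with Section 4.5 and Table 1 footnote g.

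**SAP.** Flag the randomised patients who met any of the three triggers after stability and list them by arm. State in Section 7.2 that withdrawal-criteria deviations are classified by the reconciled rule before unblinding. Optionally, repeat the primary analysis without the flagged patients as a supportive analysis. The flag is fixed before randomisation, so that analysis still compares randomised groups.

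**Cost.** Wording changes, one listing and at most one extra analysis. PANSS and CGI-S are already collected at every open-label visit, so no new data are needed.
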